15 APPENDIX

Not Applicable.

Alcon - Business Use Only Protocol - Clinical

Document: TDOC-0052880

Version: 2.0; Most-Recent; Effective; CURRENT

Status: Effective

Effective Date: 20-Dec-2016

Short Title:

**Statistical Analysis Plan
LCS739-P001**

Full Title:

**Statistical Analysis Plan
LCS739-P001 / NCT02965833**

Protocol Title: Clinical Study of CLEAR CARE® PLUS for Presbyopic Contact Lens Wearers

Project Number: LCS739-P001

Protocol TDOC Number: TDOC - 0052880

Author: [REDACTED]

[REDACTED]

Template Version: Version 4.0, approved 16MAR2015

Approvals: See last page for electronic approvals.

Job Notes:

This is the original (Version 1.0) Statistical Analysis Plan for this study. This version of the Statistical Analysis Plan is based on Version 1.0 of the study protocol.

Executive Summary:

Key Objectives:

The primary objective is to demonstrate superiority of CLEAR CARE PLUS (CCP) cleaning & disinfecting solution when compared to the subject's habitual multipurpose solution (HMPS) in reducing symptoms of contact lens induced dryness after 30 days of use, based on responses to the CLDEQ-8 (abbreviated Contact Lens Dry Eye Questionnaire).

Decision Criteria for Study Success:

Success of this study will be based on demonstration of superiority of CCP cleaning & disinfecting solution compared to habitual MPS in reducing symptoms of contact lens induced dryness after 30 days of use, based on responses to the CLDEQ-8.

Table of Contents

Statistical Analysis Plan LCS739-P001	1
Table of Contents	3
List of Tables.....	4
List of Figures	4
1 Study Objectives and Design.....	5
1.1 Study Objectives.....	5
1.2 Study Description	6
1.3 Randomization.....	8
1.4 Masking	8
1.5 Interim Analysis	9
2 Analysis Sets.....	9
2.1 Safety Analysis Set.....	9
2.2 Full Analysis Set.....	9
2.3 Per Protocol Analysis Set	9
3 Subject Characteristics and Study Conduct Summaries.....	9
4 Efficacy Analysis Strategy.....	10
4.1 Efficacy Endpoints	10
4.2 Efficacy Hypotheses	11
4.2.1 Hypothesis for the Primary Endpoint	11
[REDACTED]	12
4.3 Statistical Methods for Efficacy Analyses.....	13
4.3.1 Primary Efficacy Analyses	13
[REDACTED]	13
[REDACTED]	15
4.5 Subgroup Analyses and Effect of Baseline Factors.....	16
4.6 Interim Analysis for Efficacy	16
5 Safety Analysis Strategy	16
5.1 Safety Endpoints.....	16
5.2 Safety Hypotheses	17
5.3 Statistical Methods for Safety Analyses	17

5.3.1	Adverse Events.....	17
5.3.2	Biomicroscopy Findings.....	18
5.3.3	Device Deficiencies.....	18
6	Analysis Strategy for Other Endpoints.....	18
7	Sample Size and Power Calculations	18
8	References	19
9	Revision History.....	19
10	Appendix	20

List of Tables

1.1 Study Objectives

The overall objective of this study is to demonstrate the benefit of CCP cleaning & disinfecting solution compared to non-HydraGlyde® multipurpose contact lens solutions in presbyopes currently wearing soft contact lenses and experiencing symptoms of dryness.

PRIMARY OBJECTIVE

- To demonstrate superiority of CCP cleaning & disinfecting solution when compared to the subject's HMPS in reducing symptoms of contact lens induced dryness after 30 days of use, based on responses to the CLDEQ-8.

[figure not shown]
1.2 Study Description

This is a prospective, randomized, crossover (2-treatment, 2-period), stratified (BIOTRUE and other HMPS), observer-masked, and quasi-subject-masked study. The study population will consist of approximately 120 subjects (approximately 8 to 20 subjects per site) to be randomized at approximately 9 United States sites to achieve approximately 110 subjects completed. The expected duration of subject participation in the study (3 scheduled visits) is 30 ± 3 days per study period (up to 66 days total). Upon completing Pre-screening Questionnaire and satisfying the relevant pre-screening criteria, subjects will sign informed consent and then be considered enrolled into the study. Subjects will be randomized at Visit1, after inclusion and exclusion criteria are confirmed. The randomization will be stratified by HMPS (BIOTRUE vs. Other MPS).

Each subject will wear their habitual lens brand (following manufacture recommended replacement) on a daily wear basis for 30 ± 3 days using either CCP or their habitual solution daily to care for their lenses.

The planned visit schedule is depicted in Figure 1.2.-1.

Figure 1.2-1 Flow Diagram of Study

1.3 Randomization

A member of the Randomization Programming group at Alcon who is not part of the study team will generate the randomized allocation schedule(s) for study contact lens solution assignment. Subjects eligible after screening at Visit 1 will be randomized (1:1) to receive either CCP or HMPS to care for their lenses in Period 1 of the study. For Period 2, the contact lens solution that was not allocated for use in Period 1 will be dispensed. The randomization will be stratified by HMPS (BIOTRUE vs. Other MPS). Randomization will be blocked to ensure a balance of study treatment (lens care sequence) allocation within investigational sites and strata. Randomization will be implemented in an Electronic Data Capture (EDC) system.

1.4 Masking

This study is investigator-masked and subject quasi-masked (masked to test solution brand only), with subjects randomized to the order in which they will use CCP and their HMPS for 30 ± 3 days each. The Investigator will not be aware of the specific treatment being administered and the subject will not be aware of the brand of the test solution. Excluding the study monitor, Lead CSM, and person responsible for generating the randomization schedule, all Alcon study personnel will also be masked. This level of masking will be maintained throughout the conduct of the study. In the event of a medical emergency where the knowledge of subject treatment is required, an individual Investigator will have the ability to unmask the treatment sequence assignment for a specific subject.

1.5 Interim Analysis

No interim analyses are planned for this study.

2 Analysis Sets

2.1 Safety Analysis Set

The safety analysis set will include all subjects/eyes exposed to the newly dispensed habitual lenses for the study disinfected with at least one study lens product evaluated in this study. Safety analysis will be conducted using the safety analysis set on a treatment-emergent basis. For treatment-emergent safety analysis, subjects/eyes will be categorized under the actual lens care products exposed.

2.2 Full Analysis Set

The Full Analysis Set (FAS) will consist of all randomized subjects who are exposed to at least one of the study lens care products as defined for the Safety Analysis Set. Each subject will be classified according to the respective lens care products in the randomized lens sequence, irrespective of the exposure. FAS will serve as the primary analysis dataset for all efficacy evaluations.

2.3 Per Protocol Analysis Set

The per-protocol (PP) analysis set is a subset of all randomized subjects and excludes all data/subjects which have met any of the critical deviation or evaluability criteria identified in the Deviations and Evaluability Plan. Each subject will be classified according to the respective lens care products in the randomized lens sequence, irrespective of the exposure.

3 Subject Characteristics and Study Conduct Summaries

Demographic information (age, sex, ethnicity, race) will be summarized on the safety, full, and PP analysis sets. Baseline characteristics on habitual lens and lens care information as well as activities, CLDEQ-8, [REDACTED], [REDACTED] [REDACTED] will be summarized on the full and PP analysis sets. Due to the crossover design, demographic and baseline data will be presented by lens care sequence group and overall.

All descriptive summary statistics will be displayed with n and % for categorical data, and with mean, standard deviation, median, minimum, and maximum for continuous data.

4 Efficacy Analysis Strategy

This study defines one primary endpoint [REDACTED] The Full Analysis Set will serve as the primary set for all efficacy analyses. [REDACTED]

[REDACTED]

[REDACTED]

[REDACTED]

[REDACTED]

[REDACTED]

[REDACTED]

4.1 Efficacy Endpoints

Primary Endpoint

The primary endpoint is the score (range 0 to 37) from CLDEQ-8, obtained by adding the numerical responses to each of the 8 items, collected at the Day 30 follow up, each product (Visit 2 and Visit 3).

[REDACTED]

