5. A known sensitivity to any ingredients in CCP.
6. Biomicroscopy findings observed during the Visit 1 slit-lamp examination that are moderate (grade 3) or worse in either eye.
7. Prior refractive surgery (eg, laser assisted in situ keratomileusis [LASIK] and photorefractive keratectomy [PRK]).
8. History of herpetic keratitis, ocular surgery, or irregular cornea.

Sponsor:

Alcon Research, Ltd.
[name]

Protocol Number: LCS739-P001

9. A pathological dry eye that precludes contact lens wear.
10. Use of mechanical eyelid therapy or eyelid scrubs within 14 days before Visit 1 and not willing to discontinue during the study.
11. Enrollment of the Investigator or his/her staff, family members of the Investigator, family members of the Investigator's staff, or individuals living in the households of these individuals.
12. Enrollment of more than 1 member of the same household in the study.
13. Participation in any clinical study within 30 days of Visit 1.
14. Subjects who are currently using or have not discontinued Restasis®, Xiidra® or a topical steroid within the past 7 days.

Assessments:

- CL-induced dryness symptoms as measured by CLDEQ-8
- Symptomatology pre-screening questionnaire
- [REDACTED]
- [REDACTED]
- [REDACTED]
- [REDACTED]
- [REDACTED]
- [REDACTED]
- Biomicroscopy
- Snellen visual acuity
- AEs and device deficiencies

Statistical Methods:**Planned Analysis:**

Three analysis sets will be defined: safety, full, and per protocol (PP). The safety analysis set will include all subjects/eyes exposed to any

Sponsor:

Alcon Research, Ltd.
[name]

Protocol Number: LCS739-P001

[figure not shown]
study lens care products evaluated in this study. The full analysis set (FAS) is the set of all randomized subjects who are exposed to any study lens care products. The PP analysis set is a subset of all randomized subjects and excludes those who meet the critical deviation criteria as specified in the Deviations and Evaluability Plan (DEP). The FAS will serve as the primary analysis set for all efficacy evaluations.

All data from evaluable subjects will be included in the efficacy analysis; no imputation for missing values will be performed.

Efficacy:

To address the primary efficacy objective, planned analyses are summarized below.

Endpoint	Comparison	Statistical Method
PRIMARY		

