10.2.3 VISIT 3 – Period 2/ DAY 30 /EXIT

1	Document wear time compliance (days, hours) and lens care compliance. Collect used study lens care product(s) from the subject.
2	Obtain information on any changes in medical health and/or the use of concomitant medications since Visit 2.
3	Have subject complete the Subjective Questionnaire based on lenses worn and test solution used during the 30 day study period (CLDEQ-8, [REDACTED] [REDACTED] [REDACTED] [REDACTED])

4	Conduct Snellen VA with worn lenses. For details refer to MOP.
5	[REDACTED]
6	Remove lenses and perform biomicroscopy assessments using slit-lamp examination scales. For details and order of staining procedures, refer to MOP.
7	Perform subjective (manifest) refraction assessment and BCVA assessment (as needed). For details refer to MOP.
8	Assess and record AEs that are observed or reported (see Section 12).
9	Record any device deficiencies that are observed or reported.
10	Exit the subject from the study.

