10.4 Discontinued Subjects and Screen Failures

Discontinued subjects are those who withdraw or are withdrawn from the study after being randomized. Subjects may discontinue from the study at any time for any reason. Subjects

may also be discontinued from the study at any time if, in the opinion of the Investigator, their continued participation poses a risk to their health. Discontinued subjects will not be replaced (ie, their subject numbers will not be re-assigned/re-used).

If a subject is identified not to fulfill the eligibility criteria for study inclusion during the Screening visit (Visit 1), the subject will be screen failed and will not participate any further in the study. The EDC system will be updated to confirm the subject is a screen failure. The Investigator will explain to the subject the reason(s) why eligibility was not met and provide appropriate information/treatment, if required. The Exit form will be completed for all discontinued subjects and screen failures.

Should a subject exhibit any clinically relevant signs, symptoms, or other clinical observations that possibly could be associated with suspected sensitivity or intolerance to one of the study treatments, the Investigator must document those observations on an AE Form. Observations must also be reported for occurrences not associated with any study treatment (see Section 12.3, Procedures for Recording and Reporting AEs and SAEs).

Any subject who exits early from the study should undergo all procedures outlined at Visit 3/Exit. Additionally, the Exit Form must be completed and the reason for discontinuation must be identified and captured in EDC.

Finally, to ensure the safety of all subjects who discontinue early, Investigators should assess each subject and, if necessary, advise them of any therapies and/or medical procedures that might be needed to maintain their health.

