11.4.1 Primary Efficacy

The primary objective of this study is to demonstrate superiority of CCP when compared to habitual lens care product in reducing dryness symptomatology as measured by CLDEQ-8.

The corresponding endpoint is the score (range 0 to 37) from CLDEQ-8, obtained by adding the numerical responses to each of the 8 items, collected at the Day 30 follow-up, for each product (Visit 2 and Visit 3).

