11.5 Handling of Missing Data

All data obtained in evaluable subjects/eyes will be included in the analysis. No imputation for missing values will be carried out for the efficacy analysis.

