4.3 Statistical Methods for Efficacy Analyses

4.3.1 Primary Efficacy Analyses

A mixed effect repeated measures model will be fit to test these hypotheses, including terms for lens care solution, period, sequence group, habitual HMPS stratification (BIOTRUE, other HMPS) and baseline CLDEQ-8 as fixed effects and subject as a random effect. [REDACTED]

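### Does the plan leave open whether a CLDEQ-8 score taken at early exit enters the Day 30 primary model?

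*SAP*

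**What the plan says.** **Endpoint.** Protocol 11.4.1 defines the primary score as "collected at the Day 30 follow-up, for each product (Visit 2 and Visit 3"), and SAP 4.1 repeats this almost word for word: "collected at the Day 30 follow up, each product (Visit 2 and Visit 3"). The hypotheses in Protocol 11.4.1.1 and SAP 4.2.1 compare the two product means at the same time point.

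**Early exit.** Protocol 10.4 states: "Any subject who exits early from the study should undergo all procedures outlined at Visit 3/Exit". One of those procedures (Protocol 10.2.3, step 3) reads: "Have subject complete the Subjective Questionnaire based on lenses worn and test solution used during the 30 day study period (CLDEQ-8". Protocol 10.3 provides a separate Early Exit form for a subject who discontinues at an unscheduled visit.

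**Data included.** The synopsis says: "All data from evaluable subjects will be included in the efficacy analysis; no imputation for missing values will be performed". Protocol 11.5 says: "All data obtained in evaluable subjects/eyes will be included in the analysis", and also rules out imputation.

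**Analysis set and model.** The full analysis set needs exposure to only one product, so early leavers belong to it. SAP 2.2 adds: "Each subject will be classified according to the respective lens care products in the randomized lens sequence, irrespective of the exposure". The primary model in SAP 4.3.1 has solution, period, sequence, habitual-solution stratum and "baseline CLDEQ-8 as fixed effects and subject as a random effect". The text after that sentence is redacted. SAP 4.4 and Protocol 11.6 cannot be read either.

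**Timing of decisions.** Protocol 11.1 fixes subject evaluability before the sequence code is broken and the database is locked.

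**The concern.** A subject who leaves on, say, day 12 completes the questionnaire under procedures headed Visit 3, and so produces a CLDEQ-8 score that is not a Day 30 score. Under the endpoint definition the score is out. Under the sentence that all data are included, it appears to be in.

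A second worry follows for exits in Period 1. Visit 3 is labelled Period 2, and the full analysis set is classed by randomized sequence whatever the exposure. A score filed mechanically as Visit 3 would then count for a product the subject had not yet used.

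Study success rests on this single one-sided test (SAP Executive Summary). If the rule were truly open, someone could choose which records to use after seeing the assignments, and the type I error would rise above the nominal 5%.

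**Working it through.** **1. The passages side by side.**

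| Question | Specific text | General text | Reading |
|---|---|---|---|
| Is a score before the Day 30 window the endpoint? | Protocol 11.4.1 and 11.4.1.1, SAP 4.1 and 4.2.1: Day 30 follow-up, Visits 2 and 3 | Synopsis and Protocol 11.5: all data from evaluable subjects, no imputation | The specific definition governs; the score is not the endpoint |
| Does an exit record become Visit 3? | Protocol 10.3: separate Early Exit form for a discontinuation at an unscheduled visit | Protocol 10.4: perform the Visit 3/Exit procedures | The procedures are shared; nothing says the record is relabelled |
| Which product does an exit score describe? | Protocol 10.2.3: the questionnaire asks about the solution used in the period | SAP 2.2: subjects classed by randomized sequence | The product in use. Randomized sequence does not move a Period 1 score into Period 2 |
| When are inclusion decisions made? | Protocol 11.1: subject evaluability set before the code is broken | Protocol 11: deviations may be detailed in the study report | Subject-level choices are closed before unmasking; record-level choices are not named |

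**2. The plan's own figure.** Inputs from Protocol 11.10 and SAP 7: SD of paired differences 10, difference 3, one-sided alpha 0.05, 36 per sequence. With N = 72 the noncentrality is 3 / (10/√72) = 2.55. The noncentral t with 70 degrees of freedom gives power 0.809. N = 70 gives 0.7996, just short of 80%, so 36 per sequence is the minimum and the stated figure is reproduced. At the 110 planned completers, power is 0.931.

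**3. How many records are in question.** Protocol 8 plans about 120 randomized and 110 completed: 120 − 110 = 10 exits, or 10/120 = 8.3%.

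**4. How far the two readings differ when exits are unrelated to outcome.** Assumptions not in the documents: within-subject correlation 0.5, exits shared equally between periods and sequences, known variances, no baseline covariate. The model is generalized least squares for a two-period crossover with solution, period and sequence fixed and subject random.

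- Reading A, exit score left out: SE = 0.9483.
- Reading B, exit score used for the product and period being left: SE = 0.9276.
- B uses all the data in A plus the exit scores, so Var(A − B) = Var(A) − Var(B) = 0.9483² − 0.9276² = 0.8993 − 0.8604 = 0.0389. The SD of the difference is √0.0389 = 0.197 points.
- The correlation between the estimates is 0.9276/0.9483 = 0.978.

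Each reading rejects when z < −1.645. The bivariate normal then gives:

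| True difference | Readings give opposite verdicts |
|---|---|
| 0 | 1.7% |
| −1.57 (about −1.645 × 10/√110, the significance line) | 6.8% |
| −3 (planned) | 2.1% |

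Each reading alone has type I error 5.0%. Taking whichever is favourable after unmasking gives 5.9%. Correlations of 0.3 and 0.7 change these figures by no more than 0.1 percentage point.

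**The case for a change.** The strongest reply is that exits may not be random. Suppose all 10 exits, or 8 of the 10, are from CCP, and each leaver scores 10 points worse on the product left. With exits half in each period, correlation 0.5 and a target of no mean difference over all 120 subjects, the Day 30-only type I error is 22.2% (10/0) or 13.2% (8/2). Using the exit scores gives 7.8% or 6.6%. Filing exit scores as Visit 3 by sequence gives 16.1% or 10.5%.

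The arithmetic is sound, but it does not show a defect in the wording. The largest figures measure informative dropout under the Day 30-only analysis, which is a standard mixed model under missing at random and is the reading the plan already gives. A sentence confirming that reading would leave them untouched. The splits and the 10-point penalty are assumptions. So is the division between periods: with all 10 exits from CCP, moving them from all in Period 2 to all in Period 1 takes the misfiled figure from 5.0% to 35.9%. The misfiled case also needs an early-exit record to be credited to a product the subject had not yet used.

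Two parts of the objection stand. Protocol 11.1 fixes the evaluability of subjects, not which records of an evaluable subject enter the model, and both documents tie the Deviations and Evaluability Plan explicitly only to the per-protocol set. Nor does any visible sentence say that a Period 1 exit score belongs to Period 1. These are real gaps in detail, but each has an obvious filling.

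**Conclusion.** No change follows. The visible text omits a line that analysts would supply correctly from the endpoint definition, the hypotheses, the questionnaire wording and the separate exit form. Writing it down would confirm the Day 30-only analysis without altering the test, the data or the success rule.

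The size supports this. The chance of a different verdict is highest, at 6.8%, when the true effect sits on the significance line. The 5.9% type I error would arise only from a deliberate choice between readings after unmasking. These figures rest on 10 exits unrelated to outcome, equal division between periods and sequences, and the plan's paired SD of 10. Exits strongly lopsided by product and linked to worse scores would matter more, but that is a question about missing data, for which the documents give no figures, and not a contradiction in the text.

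The conclusion is also limited by what can be read. The redacted SAP text, the unreadable SAP 4.4 and Protocol 11.6, or the Deviations and Evaluability Plan may already state the rule, so the plan cannot be called silent.

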4.2 Efficacy Hypotheses

4.2.1 Hypothesis for the Primary Endpoint

[figure not shown]
The primary hypothesis to be tested is that CCP is superior to HMPS in reducing dryness symptomatology as measured by CLDEQ-8.

[figure not shown]
The null and alternative hypotheses for the primary efficacy endpoint are formulated as follows:

$$H_0: \mu_{(CCP)} - \mu_{(HMPS)} \geq 0$$

$$H_a: \mu_{(CCP)} - \mu_{(HMPS)} < 0$$

where $\mu_{(CCP)}$ and $\mu_{(HMPS)}$ denote the mean CLDEQ-8 score for CCP and HMPS, respectively, at the Day 30 follow-up.

[figure not shown]

[figure not shown]

4.3 Statistical Methods for Efficacy Analyses

4.3.1 Primary Efficacy Analyses

A mixed effect repeated measures model will be fit to test these hypotheses, including terms for lens care solution, period, sequence group, habitual HMPS stratification (BIOTRUE, other HMPS) and baseline CLDEQ-8 as fixed effects and subject as a random effect. [REDACTED]

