11 ANALYSIS PLAN

Continuous variables will be summarized for the observed values using the number of observations, mean, SD, median, minimum and maximum, as well as CIs or CLs where applicable. Categorical variables will be summarized with counts and percentages from each category. Any deviations to this analysis plan will be updated during the course of the study as part of a protocol amendment or will be detailed in the clinical study report.

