11.4.1.2 Analysis Methods

A mixed effect repeated measures model will be fit to test these hypotheses, including terms for lens care solution, period, sequence group, and baseline CLDEQ-8 as fixed effects and subject as a random effect. Lens care difference (CCP minus HMPS) and the corresponding one-sided 95% upper confidence limit will be provided.

Descriptive summary statistics will also be presented for the subgroup of habitual BIOTRUE formulation users.

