4.5 Subgroup Analyses and Effect of Baseline Factors

Descriptive summary statistics for the primary efficacy endpoint will be presented for the subgroup of habitual BIOTRUE formulation users. [REDACTED]

[REDACTED]

[REDACTED]

[REDACTED]

[REDACTED]

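### Does entering the BIOTRUE stratum as a main effect, with descriptive summaries for BIOTRUE users, leave the trial without a valid CCP versus BIOTRUE estimate?

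*SAP*

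**What the plan says.** SAP section 1.3 stratifies 1:1 randomization by habitual multipurpose solution and adds: "Randomization will be blocked to ensure a balance of study treatment (lens care sequence) allocation within investigational sites and strata". The protocol synopsis sets a recruitment goal that at least half of the subjects use BIOTRUE.

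The primary hypothesis in SAP section 4.2.1 is about the pooled control: "The primary hypothesis to be tested is that CCP is superior to HMPS in reducing dryness symptomatology as measured by CLDEQ-8".

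The two documents list slightly different primary models. Protocol section 11.4.1.2 has a model "including terms for lens care solution, period, sequence group, and baseline CLDEQ-8 as fixed effects and subject as a random effect". SAP section 4.3.1 adds the stratum to that list, which ends with "habitual HMPS stratification (BIOTRUE, other HMPS) and baseline CLDEQ-8 as fixed effects and subject as a random effect". Blacked-out text follows the SAP sentence.

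For BIOTRUE users, SAP section 4.5 states: "Descriptive summary statistics for the primary efficacy endpoint will be presented for the subgroup of habitual BIOTRUE formulation users". Several blacked-out lines follow under the same heading. Protocol section 11.4.1.2 has a matching sentence: "Descriptive summary statistics will also be presented for the subgroup of habitual BIOTRUE formulation users". The introduction to protocol section 11 says that summaries of continuous variables give "mean, SD, median, minimum and maximum, as well as CIs or CLs where applicable".

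**The concern.** BIOTRUE is prominent in the design: it is the stratification factor, it has a recruitment target, and the protocol's statement of purpose repeats that target. A reader would expect the analysis to say how CCP performs against BIOTRUE in particular.

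The visible model has no product-by-stratum term, and a subject-level main effect cancels from a within-subject comparison. The BIOTRUE subgroup is promised descriptive statistics. If these were separate means and SDs for each product, they would give no correct standard error for a paired difference. The control is a mix of solutions, so the pooled effect depends on the share of BIOTRUE users enrolled. If the effect differed between strata, the trial could then report a pooled benefit and leave the BIOTRUE comparison without a proper interval, although the crossover could supply one.

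**Working it through.** **1. The plan's own figure.** Inputs from protocol section 11.10: SD of paired differences 10, difference 3, one-sided α 0.05, power 80%.

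- Normal approximation: N = ((1.645 + 0.842) × 10 / 3)² = 68.7, which rounds up to 35 per sequence.
- Noncentral t with N − 2 degrees of freedom: N = 70 gives 79.96% and N = 72 gives 80.9%.

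The stated 36 per sequence is reproduced. It is sized for the pooled CCP minus HMPS contrast.

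**2. What the stratum main effect does.** Write subject i's score in period j as

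y = μ + τ·product + π·period + λ·sequence + γ·stratum + β·baseline + subject effect + error.

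Stratum, baseline, sequence and subject effect are the same in both of a subject's periods. The within-subject difference CCP − HMPS is therefore τ ± π + error, and γ and β drop out. Simulated mixed models confirm this (40 data sets of 120 subjects, assumed between- and within-subject variances of 50 each, so that the paired SD is √(2 × 50) = 10):

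| Data | Change in estimate when stratum is added | Largest change in SE | Mean SE |
|---|---|---|---|
| Complete | below 10⁻¹³ | about 0.00001 | 0.92 |
| 10 of 120 without Period 2 | mean 0.02, maximum 0.06 | 0.004 | 0.94 |

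The loss of 10 follows the plan's 120 randomized and 110 completed. The term does no harm.

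**3. What the listed model estimates.** With simulated effects of −3 in other users and −6 in BIOTRUE users, in equal numbers, the main-effect model returned about −4.4, close to the average (−3 − 6)/2 = −4.5. A model with a product-by-stratum term returned about −6.3 for BIOTRUE. The listed model gives the pooled effect, which is the quantity in the stated hypothesis.

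**4. What descriptive means give in BIOTRUE users.** For subjects with both periods, mean(CCP) − mean(HMPS) = mean(CCP − HMPS) identically. In a simulated subgroup both came to −5.547. A period effect enters only through unequal sequence numbers n₁ and n₂, in the proportion |n₁ − n₂| / (n₁ + n₂):

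- 27 and 28: 1/55 = 0.02 of the period effect.
- 30 and 25: 5/55 = 0.09 of the period effect.

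Blocking within strata keeps this imbalance small. The point estimate is sound.

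**5. Precision.** Assume 50% of 110 completers are BIOTRUE users (n = 55), with the plan's SD of 10.

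- Paired SE = 10/√55 = 1.35; two-sided 95% half-width = 2.71.
- SE built from separate product SDs as if independent = 1.35/√(1 − ρ): 1.51 at ρ = 0.2, 1.91 at ρ = 0.5, 2.46 at ρ = 0.7 (correlations assumed).

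The second set would overstate the uncertainty, but nothing in the visible plan calculates it. It arises only if a reader treats the two product summaries as independent groups.

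**6. What an interaction model could show.** With 55 subjects in each stratum, SE = 10 × √(1/55 + 1/55) = 1.91. Power for a 3-point difference between strata at two-sided 0.05 is Φ(3/1.91 − 1.96) = about 35%.

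**The case for a change.** The strongest opposing argument starts from the endpoint. SAP section 4.1 defines it as the score for each product at Visits 2 and 3, not as a within-subject difference. SAP section 3 lists mean, SD, median, minimum and maximum for continuous summaries and names no confidence interval. Read together, these suggest separate product summaries for BIOTRUE users, with no interval on the difference. The protocol's allowance for intervals where applicable does not commit anyone to produce one. A half-width of 2.71 lies inside the 3-point design difference, so the information would be useful, and specifying the model in advance would be better than a later unplanned analysis.

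Part of this stands. The visible text promises no BIOTRUE-specific difference with an interval, and adding one as supportive estimation would be cheap. It does not amount to a fault, for three reasons:

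- Whether the summaries are paired is an inference; neither document says.
- Redactions follow both the SAP model sentence and the SAP subgroup sentence, so it cannot be shown that nothing more is planned. Redacted text does not count as missing.
- No visible objective or hypothesis compares CCP with BIOTRUE. Stratifying to balance sequences does not oblige anyone to make subgroup inferences, and descriptive reporting is a defensible choice when the trial is sized for the pooled contrast.

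The protocol and SAP do differ on whether the stratum is in the model. That is a separate matter of wording. By step 2 it has no effect on the complete-data result and a negligible one with the planned dropout.

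**Conclusion.** The concern does not hold. The stratum main effect matches the stratified randomization and leaves the primary contrast intact: exactly so with complete pairs, and within 0.06 points in simulations with the planned dropout. The primary hypothesis and sample size are unaffected. The descriptive plan yields a valid point estimate for BIOTRUE users with both periods, with any period effect diluted to 0.02 to 0.09 of its size at the sequence splits examined.

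What remains is a preference for one more supportive table. Its stratum-specific interval would be about ±2.7 points, and its interaction test would have about 35% power for a 3-point difference.

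These sizes assume the plan's paired SD of 10, 55 BIOTRUE completers out of 110, and the equal variance components used in the simulations. The equality of mean differences applies to completers; subjects with only one period would disturb it slightly. Whether the redacted SAP text already contains a stratum-specific analysis cannot be determined.
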